10.2.2 Listing of AEs

The following additional listings will be prepared. Both ATG-Day 1 treatment group and ATG-Dynamic treatment group prior to AE start date will be included in the listing.

- List of all TEAEs by resection cohort, ATG-Day 1 treatment group and subject ID
- Listing of all serious TEAEs by resection cohort, ATG-Day 1 treatment group and subject ID
- Listing of all TEAEs that led to discontinuation of study drug by resection cohort, ATG-Day 1 treatment group and subject ID
- Listing of all fatal TEAEs
- Listing of all AEs in the safety follow-up period, by resection cohort, ATG-Day 1 treatment group and subject ID
- Listing of all deaths by resection cohort, ATG-Day 1 treatment group and subject ID
- List of subject numbers associated with each PT for all AEs assessed by the investigator as having a reasonable possibility of being related to study drug by resection cohort, ATG-Day 1 treatment group.

10.3 Analysis of Laboratory Data

Laboratory test variables as well as their statistical analysis methods including hematology, chemistry, urinalysis, and additional test variables are specified in Table 4. The analyses will be performed in both the resected and non-resected population using the population and treatment groups as described in Table 1 in Section 4.2.

Table 4. Laboratory Variable and Corresponding Statistical Analyses

Laboratory Test Variables		
Hematology	Hematocrit	
	Hemoglobin	
	Red blood cell (RBC) count	
	White blood cell (WBC) count	
	Neutrophils	
	Bands	
	Lymphocytes	
	Monocytes	
	Basophils	
	Eosinophils	
	Platelet count (estimate not acceptable)	
Urinalysis	Specific gravity	
	Ketones	
	pH	
	Protein	
	Blood	
	Glucose	
Clinical Chemistry	Blood urea nitrogen (BUN)	
	Creatinine	
	Total bilirubin	
	Pre-albumin	
	Albumin	
	Alanine transaminase (ALT)	
	Aspartate transaminase (AST)	
	Alkaline phosphatase	
	Sodium	
	Potassium	
	Calcium	

Table 4.Laboratory Variable and Corresponding Statistical Analyses
(Continued)

Laboratory Test Variables		
Clinical Chemistry (continued)	Inorganic phosphorus	
	Uric acid	
	Cholesterol	
	Total protein	
	Glucose	
	Triglycerides	
	Bicarbonate/CO2	
	Chloride	
Other Tests	Nutritional Biomarkers	

For all the laboratory parameters, the mean change from baseline to Week 13 visit (the final post-baseline) will be summarized with descriptive statistics.

Where it is applicable to categorize a laboratory assessment by Normal, High, or Low according to the normal range provided by the central laboratory, changes in laboratory parameters will be tabulated using shift tables categorized as low, normal, or high based on the normal ranges of the laboratory used for each sample. A shift table from baseline to the minimum and maximum value during treatment will be created by the analysis treatment groups described above.

10.4 Analysis of Vital Signs and Weights

The mean change from baseline to Week 13/EOT visit in vital signs, will be summarized for both resected and non-resected population. Vital sign variables include systolic blood pressure (SBP), diastolic blood pressure (DBP), pulse rate, body temperature.

11.0 Interim Analyses

No Interim analysis is planned.

12.0 Overall Type-I Error Control

The primary endpoint will be tested for each treatment group (high dose, low dose) in resected population separately at 2-sided alpha level of 0.05. Multiplicity adjustment is not planned for the primary endpoint analysis, as well not planned for any secondary endpoint analysis, as this study is not intent for registrational purpose or drug label enhancement.

13.0 Version History

Table 5.SAP Version History Summary

Version	Date	Summary
1.0	13 December 2020	Original version

Appendix A. Protocol Deviations

The number and percentage of subjects who reported at least one of the following protocol deviation categories will be provided.

- Subject entered into the study even though s/he did not satisfy entry criteria.
- Subject developed withdrawal criteria during the study and was not withdrawn.
- Subject received wrong treatment or incorrect dose of study.
- Subject took prohibited concomitant medication.

Appendix B. Quality of Life (QoL) (EORTC QLQ-C30 and QLQ PAN 26)

The QLQ-C30 is composed of both multi-item scales and single-item measures. These include five functional scales, three symptom scales, a global health status / QoL scale, and six single items. Each of the multi-item scales includes a different set of items - no item occurs in more than one scale.

All of the scales and single-item measures range in score from 0 to 100. A high scale score represents a higher response level.

Thus, a **high raw score for a functional scale** represents a *high / healthy level of functioning*, a **high score for the global health status / QoL** represents a *high QoL*, but a **high score for a symptom scale / item** represents a *high level of symptomatology / problems*.

The principle for scoring these scales is the same in all cases:

- To estimate the average of the items that contribute to the scale; this is the raw score.
- To use a linear transformation to standardize the raw score, so that scores range from 0 to 100; a higher score represents a higher ("better") level of functioning, or a higher ("worse") level of symptoms.

In practical terms, if items I₁, I₂, In are included in a scale, the procedure is as follows.

Raw Score

We calculate the raw score as follows:

Raw Score = RS = (I1 + I2 + ... + In)/n

Linear Transformation

Then linear transformation is applied to 0-100 to obtain the score S.

Functional Scales:

$$S = \left\{\frac{RS - 1}{range}\right\} * 100$$

Symptom Scales / items:

$$S = \left\{1 - \frac{RS - 1}{range}\right\} * 100$$

Global health status / QoL:

$$S = \left\{\frac{RS - 1}{range}\right\} * 100$$

Range is the difference between the maximum possible value of *RS* and the minimum possible value. The QLQ-C30 has been designed so that all items in any scale take the same range of values. Therefore, the range of RS equals the range of the item values. Most items are scored 1 to 4, giving *range* = 3. The exceptions are the items contributing to the global health status / QoL, which are 7-point questions with *range* = 6.

	Scale	Number of items	Item Range	Version 3.0 Item numbers
Global health status / QoL				
Global health status / QoL	QL2	2	6	29,30
Functional Scales				
Physical Functioning	PF2	5	3	1 to 5
Role Functioning	RF2	2	3	6,7
Emotional Functioning	EF	4	3	21 to 24
Cognitive Functioning	CF	2	3	20,25
Social Functioning	SF	2	3	26,27
Symptom Scales / items				
Fatigue	FA	3	3	10,12,18
Nausea and vomiting	NV	2	3	14,15
Pain	PA	2	3	9,19
Dyspnoea	DY	1	3	8
Insomnia	SL	1	3	11
Appetite loss	AP	1	3	13
Constipation	СО	1	3	16
Diarrhea	DI	1	3	17
Financial Difficulties	FI	1	3	28

Table 6.Scoring the QLQ-C30

QLQ-PAN-26, the pancreatic cancer module, is designed for patients at all disease stages undergoing surgical resection, palliative surgical intervention, endoscopic palliation or palliative chemotherapy (Fitzsimmons *et al.*, 1999a,b). The module comprises 26 questions hypothesized as 17 scales and single items specifically related to pancreatic disease symptoms, treatment side-effects, and emotional issues. The scores for QLQ-PAN-26 are calculated in the same way as QLQ-C30.

Score after Linear transformation for each scale:

$$S = \left\{\frac{RS - 1}{range}\right\} * 100$$

where, RS is the Raw Score as described above.

A high score will represent a high level of disease symptoms/problems. The QLQ-PAN-26 has been designed so that all items in any scale take the same range of values. Therefore, the range of *RS* equals the range of the item values. All items are scored 1 to 4, giving range = 3.

	Scale	Number of items	Item Range	Item numbers
Pancreatic Pain	РР	4	3	31,33 to 35
Bloating	BO	1	3	32
Gastrointestinal	GA	2	3	36,37
Taste Loss	TL	1	3	38
Indigestion	IN	1	3	39
Flatulence	FL	1	3	40
Weight	WE	1	3	41
Weak Limbs	WL	1	3	42
Dry Mouth	DM	1	3	43
Jaundice	JA	2	3	44,45
Altered Bowel Habit	AB	2	3	46,47
Poor Body Image	PB	2	3	48,49
Side Effects of Treatment	SI	1	3	50
Future Health Concern	FH	1	3	51
Forward Planning limited	FP	1	3	52
Satisfaction with Health Care	SA	2	3	53,54
Sexual dissatisfaction	SX	2	3	55,56

Table 7.Scoring the QLQ-PAN-26

Appendix C. Missing Data Imputation of Quality of Life (QoL) (EORTC QLQ- C30 and QLQ PAN 26

If 50% or less are unanswered for each functioning, assume that the missing items have values equal to the average of those items which are present for that functioning. The missing items are simply ignored when making the calculations. For example, if a functioning (ith functioning with scores Q_{ij} to the jth question) has range 4 and one of the item (I_{i3}) is missing. Then, following the rule, the raw score for that function will be calculated as:

Raw score (*RS*) =
$$(I_{11} + I_{12} + I_{14})/3$$

Functioning Scale Score (S) = $\left\{1 - \frac{RS - 1}{3}\right\} * 100$

However, if more than 50% of the questions are unanswered, the score for that functioning will be left missing. The single item measures, if missing, cannot be imputed as well.

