### EORTC QLQ-C30 (version 3)

We are interested in some things about you and your health. Please answer all of the questions yourself by circling the number that best applies to you. There are no "right" or "wrong" answers. The information that you provide will remain strictly confidential.

Please fill in your initials:

--	--	--	--	--

Your birthdate (Day, Month, Year):

--	--	--	--	--	--	--	--	--	--

Today's date (Day, Month, Year):

31 

--	--	--	--	--	--	--	--	--	--

	Not at All	A Little	Quite a Bit	Very Much
1. Do you have any trouble doing strenuous activities, like carrying a heavy shopping bag or a suitcase?	1	2	3	4
2. Do you have any trouble taking a long walk?	1	2	3	4
3. Do you have any trouble taking a short walk outside of the house?	1	2	3	4
4. Do you need to stay in bed or a chair during the day?	1	2	3	4
5. Do you need help with eating, dressing, washing yourself or using the toilet?	1	2	3	4

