### EORTC QLQ - PAN26

Patients sometimes report that they have the following symptoms or problems. Please indicate the extent to which you have experienced these symptoms or problems during the past week. Please answer by circling the number that best applies to you.

During the past week:	Not at all	A little	Quite a bit	Very much
31. Have you had abdominal discomfort?	1	2	3	4
32. Did you have a bloated feeling in your abdomen?	1	2	3	4
33. Have you had back pain?	1	2	3	4
34. Did you have pain during the night?	1	2	3	4
35. Did you find it uncomfortable in certain positions (e.g. lying down)?	1	2	3	4
36. Were you restricted in the types of food you can eat as a result of your disease or treatment?	1	2	3	4
37. Were you restricted in the amounts of food you could eat as a result of your disease or treatment?	1	2	3	4
38. Did food and drink taste different from usual?	1	2	3	4
39. Have you had indigestion?	1	2	3	4
40. Were you bothered by gas (flatulence)?	1	2	3	4
41. Have you worried about your weight being too low?	1	2	3	4
42. Did you feel weak in your arms and legs?	1	2	3	4
43. Did you have a dry mouth?	1	2	3	4
44. Have you had itching?	1	2	3	4
45. To what extent was your skin yellow?	1	2	3	4
46. Did you have frequent bowel movements?	1	2	3	4
47. Did you feel the urge to move your bowels quickly?	1	2	3	4
48. Have you felt physically less attractive as a result of your disease and treatment?	1	2	3	4

Please go to the next page

During the past week:	Not at all	A little	Quite a bit	Very much
49. Have you been dissatisfied with your body?	1	2	3	4
50. To what extent have you been troubled with side-effects from your treatment?	1	2	3	4
51. Were you worried about your health in the future?	1	2	3	4
52. Were you limited in planning activities in advance (e.g. meeting friends)?	1	2	3	4
53. Have you received adequate support from your health care professionals?	1	2	3	4
54. Has the information given about your physical condition and treatment been adequate?	1	2	3	4
55. Have you felt less interest in sex?	1	2	3	4
56. Have you felt less sexual enjoyment?	1	2	3	4

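### The QLQ-C30 functional and symptom scoring formulas are exchanged in SAP Appendix B, so 14 of the 15 scales run opposite to their stated direction

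*SAP*

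**What the plan says.** SAP Section 9.4.5 sends the scoring of both questionnaires to Appendix B. Appendix B defines the raw score RS as the mean of the items in a scale and then transforms it linearly to 0–100, so that "a higher score represents a higher ('better') level of functioning, or a higher ('worse') level of symptoms". It gives three formulas:

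- Functional scales: S = {(RS − 1)/range} × 100
- Symptom scales and items: S = {1 − (RS − 1)/range} × 100
- Global health status/QoL: S = {(RS − 1)/range} × 100

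Appendix C, on missing items, works an example for a functioning scale with S = {1 − (RS − 1)/3} × 100.

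The questionnaire is reproduced in Appendix B of the Operations Manual (Protocol Appendix F). Items 1–28 run from 1 (*Not at All*) to 4 (*Very Much*) and ask about difficulties. A physical functioning item reads "5. Do you need help with eating, dressing, washing yourself or using the toilet".

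For QLQ-PAN26, SAP Appendix B says that scoring follows QLQ-C30, gives the formula {(RS − 1)/range} × 100 for every scale, and adds: "A high score will represent a high level of disease symptoms/problems". One of those scales is Satisfaction with Health Care (items 53 and 54), whose first item is "Have you received adequate support from your health care professionals".

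**The concern.** On items 1–28 a high answer is always the bad answer, for functional and symptom scales alike. To make a high functional score mean good functioning, the functional formula has to reverse the raw score. To make a high symptom score mean more symptoms, the symptom formula must not. Appendix B does each the wrong way round. Its remark that a high raw functional score is healthy carries the same mistake in words.

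QoL is a secondary endpoint in Protocol Section 3.3. Programmed as written, QLQ-C30 tables would show benefit as harm, or harm as benefit, on diarrhoea, appetite loss, nausea and vomiting, and every functional scale. Because Appendices B and C disagree, a functional scale could also be scored in one direction for complete responders and in the other for subjects with a missing item.

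**Working it through.** The plan gives no worked score for a complete scale, so what can be tested is whether its formulas deliver its stated direction.

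**Inputs**
- Intended direction: 100 = best functioning, 100 = worst symptoms, 100 = best global QoL (SAP Appendix B).
- RS = item mean, with no recoding described. Range = 3 for items scored 1–4 and 6 for the two global items (SAP Appendix B).
- Item direction: items 1–28 run from 1 (no problem) to 4 (worst); items 29–30 from 1 (very poor) to 7 (excellent) (Operations Manual Appendix B).
- Scales: 5 functional, 9 symptom scales or items, 1 global. Together they use each of items 1–30 once (SAP Table 6).

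**The two formulas.** Let U = (RS − 1)/range × 100 and R = {1 − (RS − 1)/range} × 100 = 100 − U. With range 3:

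| RS | U (Appendix B, functional) | R (Appendix B, symptom; Appendix C, functional) |
|---|---|---|
| 1 (no problem) | 0 | 100 |
| 2 | 33.3 | 66.7 |
| 3 | 66.7 | 33.3 |
| 4 (worst) | 100 | 0 |

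**Direction by scale type**
- Functional: a subject with no trouble on any item (RS = 1) gets U = 0 and the worst subject (RS = 4) gets 100. The text requires 100 and 0. All 5 are inverted.
- Symptom: a symptom-free subject (RS = 1) gets R = 100 and the worst (RS = 4) gets 0. The text requires 0 and 100. All 9 are inverted.
- Global: RS = 7 gives (7 − 1)/6 × 100 = 100 and RS = 1 gives 0. This is correct.

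Inverted: 5 + 9 = 14 of 15.

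**Effect on change from Baseline.** Since R = 100 − U, each affected level becomes 100 minus the intended score, each change has its sign reversed, and standard deviations are unchanged. Diarrhoea easing from 4 to 2:
- Appendix B as written: 66.7 − 0 = +66.7
- In the stated direction: 33.3 − 100 = −66.7

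**Appendix B against Appendix C.** A functional RS of 2.0 scores 33.3 under B and 66.7 under C. Answers of 2, 2 and 1 give RS = 5/3 = 1.67, which scores 22.2 under B and 77.8 under C. If the two were used side by side, a subject with RS = 2.0 at both visits, complete at one and missing an item at the next, would show a change of 66.7 − 33.3 = +33.3 where there was none.

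**QLQ-C30 against QLQ-PAN26.** QLQ-C30 diarrhoea answered 4 scores R = 0. QLQ-PAN26 altered bowel habit answered 4 and 4 scores U = 100. The SAP says both instruments are scored alike and that high means worse on both.

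**Satisfaction with Health Care.** Answers of 4 and 4 score 100 and mean that support and information were adequate. The formula suits the scale's name; the general statement that high means more problems is wrong for it.

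**After exchanging the two Appendix B formulas.** Functional scores run from 100 (no trouble) to 0, symptom scores from 0 (none) to 100, and the global scale is unchanged. All 15 scales then match the stated direction.

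**The case against.** The strongest reply concerns consequences, since the contradiction itself is plain in the text.

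- **Standing.** SAP Section 3.3 lists QoL as an additional endpoint and Section 9.4.5 plans descriptive statistics only. Dose modification uses three EPI Symptom Questionnaire items (SAP Section 2.5), not the QLQ. SAP Section 12.0 says the study is not meant for registration or labelling. All of this stands: the primary endpoint, power and dosing are untouched.
- **Reversibility.** The error maps S to 100 − S, loses no data and can be undone later. True, provided somebody notices it.
- **Literal programming.** Appendix B states the intended direction in words, and Appendix C's functional formula agrees with it, so a programmer might correct the slip. But Section 9.4.5 points to Appendix B for scoring, and Section 9.2.5 invokes the scoring manual only for missing items. Nothing in the plan directs the programmer away from the written formulas.
- **Missing items.** Appendix C may be only a worked example rather than a second rule, and missing items should be few: the questionnaires are electronic (Protocol Section 5.9) and sites are to see that every item is answered (Operations Manual Section 3.5). The mixing of directions is therefore conditional and probably uncommon. The inversion on complete questionnaires is neither.
- **Scope.** The reversed signs are confined to QLQ-C30. The QLQ-PAN26 formula is right for its problem-worded items, and there only the interpretive sentence about satisfaction needs correcting.

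**Conclusion.** The concern holds. As written, Appendix B inverts 14 of the 15 QLQ-C30 scales (5 functional and 9 symptom), and this follows from the SAP and the protocol's copy of the questionnaire alone. Levels are reported as 100 minus the intended score and every change from Baseline on those scales has the wrong sign. Only global health status/QoL is correct. Appendix C contradicts Appendix B on functional scales, by 33.3 points at RS = 2.

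This rests on two assumptions: that items are analysed as coded on the form, since no recoding is described, and that Appendix B is programmed literally. The damage is limited to the direction of descriptive tables, but those tables are the only planned analysis of QoL. The error should be corrected before any QoL table is produced.

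**What to change.** In SAP Appendix B:
- Score functional scales as {1 − (RS − 1)/range} × 100 and symptom scales and items as {(RS − 1)/range} × 100. Leave the global formula as it is.
- Correct the sentence that treats a high raw functional score as healthy; it is the transformed score that should be.
- For QLQ-PAN26, say that its scales use the same formula as QLQ-C30 symptom scales, and that a high Satisfaction with Health Care score is favourable.

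In SAP Appendix C, keep the functional formula, which then agrees with Appendix B. Correct the reference to a range of 4, since the formula divides by 3 and Appendix B gives the range as 3. State that the transformation is the same whether or not an item is missing.

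The cost is a few lines of SAP text and a check of any scoring code already written. No data collection or protocol change is needed.

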Appendix D.Questions from the EPI Questionnaire Considered for Dose
Modification

Exocrine Pancreatic Insufficiency (EPI) Symptom Questionnaire

Instructions: These questions ask about symptoms you may have had during the **past 7 days**. Please answer all questions by selecting the one option that best describes your experience.

1. Rate your **foul smelling stools** during the past 7 days.

□None

□Mild

□Moderate

□Severe

□Very Severe

2. Rate your **greasy or fatty stools** during the past 7 days.

□None

 \Box Moderate

Severe

□Very Severe

3. Rate your **diarrhea** during the past 7 days.

□None

□Mild

 \Box Moderate

□Severe

□Very Severe
